2.9. Glucose-lowering effect will be measured by HbA1c and fasting blood glucose

# 3. Outcomes for the exploratory objectives:

- 3.1. Plasma volume will be estimated [ePV] by Strauss estimation:
  - a.  $([{Hb_{baseline}/Hb_{end}} \times {(100-Ht_{end})/(100-Ht_{baseline})}]-1) \times 100$
- 3.2. Relationship between proximal renal tubular natriuretic effects and volume reduction: proximal renal tubular natriuretic effects will be evaluated by lithium clearance FE(Li+); volume change will be measured using the following outcome:
  - a. Estimated plasma volume (ePV)
    - *i.* Estimated percent change by Strauss estimation
  - $([{Hb_{baseline}/Hb_{end}} \times {(100 Ht_{end})/(100 Ht_{baseline})}] 1) \times 100$
- 3.3. Relationship between proximal renal tubular natriuretic effects and kidney function: proximal renal tubular natriuretic effects will be evaluated by lithium clearance FE(Li+); Kidney function will be measured using measured GFR.
- 3.4. Relationship between volume and SNS activation: Volume will be measured by ePV. Hormones will be measured by:
  - a. Neurohormones: Plasma aldosterone and renin
  - b. SNS markers: norepinephrine, epinephrine, dopamine, heart rate, heart rate variability (SDNN and RMSSD)
- 3.5. Relationship between neurohormones and volume markers with kidney function. Hormones will be measured by serum aldosterone and renin. Volume will be measured by ePV. Absolute measure of renal function outcomes is measured by measured GFR.
- 3.6. Relationship between arterial stiffness and neuro-hemodynamic & volume markers. Arterial stiffness outcomes will be measured by radial, aortic and carotid AIx, carotid-radial PWV and carotid-femoral PWV. Neuro-hemodynamic and volume markers will be measured by:
  - a. Seated: SBP, DBP, and MAP
  - b. NICOM: SBP, DBP, and MAP (chronic change only)
  - c. SNS: epinephrine, norepinephrine, dopamine, heart rate, heart rate variability (SDNN and RMSSD)
  - d. Neurohormones: Plasma aldosterone and renin
  - e. Volume will be measured by ePV
- 3.7. Relationship between neurohormones & volume markers and blood pressure. Hormones will be measured by plasma aldosterone and renin. Volume will be measured by ePV. Seated and NICOM (chronic change only) measures of SBP, DBP, and MAP will be the blood pressure outcomes.
- 3.8. The blood and urine biomarkers are:
  - a. Plasma chemistry:
    - *i.* Sodium, potassium, urea, phosphate, chloride, calcium
    - ii. AST, ALT, ALP, amylase
    - iii. Hemoglobin, hematocrit, creatinine, total bilirubin, albumin, bicarbonate,
    - iv. Glucose
  - b. Urine chemistry
    - *i.* Spot: UACR, albumin, creatinine

- *ii.* Spot: urea, protein, potassium, sodium normalized to urine creatinine
- *iii.* 24-hour urine: total volume, albumin, protein, creatinine, UACR, urea, urate, potassium, sodium, glucose

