3.3 Anticipated Outcomes

- 1. We hypothesize that dapagliflozin will result in a significant reduction in systolic and diastolic blood pressure in a cohort of KTR with or without T2D and PTDM.
- 2. We hypothesize that dapagliflozin will be well tolerated in KTR with or without T2D and PTDM, with adverse events similar to that of non-transplant populations. We also hypothesize that there will be no clinically significant changes in CNI levels or episodes of acute rejection in KTR treated with dapagliflozin vs. placebo during the study.
- 3. We hypothesize that dapagliflozin will result in a significant natriuresis, as well as reductions in arterial stiffness, albuminuria, allograft hypoxia and markers of oxidative stress, while having neutral effects on cardiac and renal function over the course of the 12-week study period.
- 4. We hypothesize that the glucose-lowering effects of dapagliflozin will be modest in KTR with T2D or PTDM due the high prevalence of CKD in this population. In participants without T2D or PTDM, we do not expect any glucose lowering.

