6. TREATMENT OF SUBJECTS

6.1 Investigational Product/Treatment

Dapagliflozin and matching placebo will be provided in 35 cc bottles, and the sponsor will be responsible for labelling. Each bottle of IP will be identified with a unique Composite ID in order to maintain the blind. By way of an Unblinding List, Pharmacy will provide treatment allocations of each Composite ID. The Unblinding List will be maintained within a secure location in the Pharmacy. Blinded personnel will not have access to this list. The blind must not be broken during the course of the study unless breaking the blind is required to provide medical care to the subject in the event of a medical emergency. The decision to break the blind is the responsibility of the Investigator. The Investigator may obtain treatment assignment directly from the unblinded Pharmacist. The Unblinding List will be used to confirm treatment assignment in the event of a medical emergency. Patients will take 10 mg dapagliflozin (1 tablet 10 mg once daily) or matching placebo according to randomised treatment scheme.

Study participants will be allocated to receive either 10 mg daily of dapagliflozin or a matching placebo for 12 weeks in a 1:1 ratio. Participants with diabetes will continue on existing medical therapy for glycemic control as recommended by Diabetes Canada⁷⁵. The study design is shown in **Figure 3.** The study investigator can titrate dapagliflozin down to 5 mg in the event that dapagliflozin 10 mg dose is not well tolerated by the participant. However, in the event of hypoglycemia, a decrease in dose of other glucose lowering therapies (including insulin), will be first initiated, if applicable, by the study investigator prior to down-titration of dapagliflozin. Every effort will be made to keep the dose of dapagliflozin constant at 10mg daily.

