9.1.2 Secondary study parameters/endpoints

The secondary outcomes of this study include metabolic, vascular, renal and transplant-specific measures. These outcomes have been included to elucidate the potential mechanisms responsible for blood pressure lowering, and putative cardio- and renoprotective effects in KTR. Safety outcomes (described further below) will also be assessed. The time points and specific measurements of secondary outcomes are shown in **Table 2**.

Metabolic outcomes: Glycemic control will be measured using the following methods: Fasting blood glucose, HbA1c and home glucose monitoring. Home glucose monitoring will be performed in patients with T2D/PTDM during 2 discrete 14 day periods during the study using the participants' usual glucose monitoring device. These two discrete 14 day periods are as follows: 1) Starting 7 days prior to drug administration and stopping 7 days after drug administration (week -1 to 1); and 2) Starting 7 days prior to drug discontinuation, and stopping 7 days after during drug discontinuation (week 11 to 13). The rationale for home glucose monitoring is to study the impact of SGLT2i on blood glucose dynamics in this unique population with variable degrees of renal impairment, concomitantly treated with diabetogenic immunosuppressive medications such as glucocorticoids and CNIs. Although the impact of CNIs on the expression of SGLT2 in human kidney allografts is not known, changes to the proximal tubular epithelial cell have been well documented with use of CNIs in KTR⁶². Urinary glucose excretion will also be measured using a 24-hour urine collection for glucose. Lastly, height, weight, waist circumference and fasting lipid profile will also be measured.

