## 2. Secondary objectives:

2.1. We will characterize the safety of dapagliflozin use compared to placebo.

We will determine acute and chronic effects of dapagliflozin vs. placebo from baseline on:

- 2.2. Calcineurin inhibitors (CNI) levels, a class of immunosuppressants measured by tacrolimus or cyclosporine
- 2.3. Systemic hemodynamics
- 2.4. Total and proximal renal tubular natriuresis measured by sodium/lithium clearance
- 2.5. Sympathetic nervous system (SNS) activation
- 2.6. Metabolic parameters
- 2.7. Kidney function indicated by iohexol-measured and estimated glomerular filtration rate (GFR)
- 2.8. Neurohormones
- 2.9. Glucose-lowering effects

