#### 5. Pre-specified post-hoc analyses:

- 5.1. The same models described in the analysis of primary objective 1.1 will be performed for the outcome.
- 5.2. The same models described in the analysis of exploratory objective 3.2 will be completed for each of the different outcomes.

Analysis population: The intention to treat population will be used for all analyses.

*Hypothesis testing:* For hypothesis testing, a 5% significance level will be used (two-sided). No interim analyses will be performed. For secondary objectives, nominal p-values will be reported.

*General model assumptions and model diagnostic procedures:* For the linear mixed-effects models with visit and treatment-by-visit interaction as covariates, a participant-level random intercept will be included. Restricted-maximum-likelihood will be used for estimation and the missing-at-random framework will be assumed. Plots of marginal and conditional residuals will be used for model diagnostics and assessment. Similar diagnostic procedures will be used for the linear regression models.

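### SAP 2.9 leaves the planned home glucose data unanalysed, puts HbA1c into the 1-week model, and gives the estimate in participants with diabetes only exploratory status

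*SAP*

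**What the plan says.** Protocol 3.2 (item 3) sets the glucose objective at 12 weeks, in all 52 recipients with or without T2D or PTDM. Protocol 3.3 (item 4) expects modest lowering with diabetes and adds: "In participants without T2D or PTDM, we do not expect any glucose lowering".

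Protocol 9.1.2 lists three glycaemic measures: "Fasting blood glucose, HbA1c and home glucose monitoring". On the third it says: "Home glucose monitoring will be performed in patients with T2D/PTDM during 2 discrete 14 day periods during the study". One period runs from 7 days before to 7 days after the first dose, the other from 7 days before to 7 days after the last. Table 2 schedules both.

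SAP Outcomes 2.9 keeps two of the three: "Glucose-lowering effect will be measured by HbA1c and fasting blood glucose". The parent heading in SAP Objectives 2 reads: "We will determine acute and chronic effects of dapagliflozin vs. placebo from baseline on". Section 2 of the analysis part applies the models of 1.1 (Visits 3 and 4 for acute, Visits 3 and 9 for chronic), which carry no diabetes term. On the analysis set the SAP states: "The intention to treat population will be used for all analyses".

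The SAP limits NICOM (Outcomes 2.3) and blood urea (analysis 3.8) to the chronic change. It makes no such exception for HbA1c. SAP section 4 plans analyses by diabetes status with an interaction test and includes the secondary objectives, under an exploratory heading.

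Background glucose-lowering treatment can change during the trial. Protocol 6.1 states: "in the event of hypoglycemia, a decrease in dose of other glucose lowering therapies (including insulin), will be first initiated". Protocol 6.2 allows further individual adjustment.

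**The concern.** There are three related gaps.

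First, the protocol specifies a measure, gives a reason for it and times it to the week before and the week after the first dose. The SAP then neither analyses it nor says why it is left out.

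Second, the SAP adds a 1-week analysis to an objective that the protocol sets at 12 weeks, and sends HbA1c through it by default.

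Third, the only estimate with secondary status averages over a group in which the protocol expects a response and a group in which it expects none, and the documents set no target for the mix. The resulting number depends on who happens to enrol. Without the stratum estimates beside it, it is hard to carry over to patients with diabetes or to those without.

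At stake is what the trial can conclude about glucose. The primary blood pressure result is not affected.

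**Working it through.** **The plan's own figure.** No sample size or power is stated for the glucose objective. The only size comes from systolic pressure in Protocol 5.3 (6.5 mmHg, SD 8, two-sided alpha 0.05, power 80%): n per arm = 2 × (1.960 + 0.842)² × 8² / 6.5² = 23.8, so 24 per arm and 48 in total. This reproduces the plan, and 24 per arm is used below.

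**Inputs for the dilution.**
- Effect without diabetes: 0 (Protocol 3.3).
- Effect with diabetes, high case: HbA1c 0.84 points, SD 1.2, from the uncontrolled series of 10 recipients on canagliflozin (Protocol 2.5).
- Effect with diabetes, low case: medians of -0.2 and +0.1 in the placebo-controlled empagliflozin trial in PTDM (Protocol Table 1), a difference of about 0.3. Its SD is not given; 0.5 and 0.8 are assumed.
- Diabetic share p: not set for this trial. Assumed 30-65%, from the population figures in Protocol 4 (T2D as cause of ESRD in about 30-40%, PTDM in about 25%; 40 + 25 = 65).
- SD of change without diabetes: not in the documents. Assumed at 0.25 to 1.0 times the diabetic SD.

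**Formulas.** Pooled effect = p × diabetic effect + (1 - p) × 0. Arm variance = p × SD² + (1 - p) × SD₀², plus p(1 - p) × effect² in the treated arm, averaged over the two arms. Power is from the noncentral t distribution at 24 per arm pooled, or 24p per arm (rounded) in diabetes only. This approximates the SAP's mixed model by a two-sample comparison of changes.

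**Results, effect 0.84, SD 1.2.**

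| Share p | Pooled effect | Pooled power | Diabetes only: n per arm | Diabetes only: power |
|---|---|---|---|---|
| 0.30 | 0.25 | 11-21% | 7 | 23% |
| 0.40 | 0.34 | 15-27% | 10 | 32% |
| 0.50 | 0.42 | 21-34% | 12 | 37% |
| 0.65 | 0.55 | 32-44% | 16 | 48% |

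**Results, effect 0.30.** The pooled effect is 0.09, 0.12, 0.15 and 0.20 at the same shares. With SD 0.5, pooled power is 9-35% and diabetes-only power 18-38%. With SD 0.8, the figures are 7-17% and 10-18%.

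The pooled figure is therefore smaller than the diabetic effect by a fraction 1 - p, that is 35% to 70%. When the SD without diabetes is small (ratio 0.25), pooled and diabetes-only power differ by at most 5 percentage points. When the SDs are equal and the effect is 0.84, diabetes-only power is 12 to 17 points higher.

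**The 1-week HbA1c model.** The documents give no time course for HbA1c, so what is lost at one week cannot be computed. The argument rests on comparing the texts: the protocol objective is at 12 weeks, the SAP adds one week, and it makes exceptions for other outcomes but not for this one.

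**Home glucose.** The weeks -1 to 1 window in Protocol 9.1.2 covers the same interval as the SAP's change from Visit 3 to Visit 4. A search of SAP Outcomes 1-5 and analyses 0-5 finds no home glucose variable. Plasma glucose and 24-hour urine glucose appear, but only as exploratory chemistry (Outcomes 3.8).

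**The case against.** The strongest reply is that pooling is what the protocol asks for. Its objective names recipients with or without diabetes, and the treatment-by-visit coefficient in the ITT population estimates that average. This stands. A reader might infer that the pooled estimate is biased or simply wrong. It is neither: it is smaller than the effect in participants with diabetes because it answers a different question. Replacing the population outright would change the estimand and would need the protocol objective changed too.

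A diabetes-specific estimate with an interaction test is already prespecified, and randomisation is stratified on T2D and PTDM status (Protocol 9.2), which supports that comparison. Secondary p-values are nominal, so the exploratory label affects prominence rather than error control. This also stands, and it reduces the third gap to one of presentation.

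A reader might infer that pooling will miss an effect that a diabetes-only analysis would find. The figures do not support this: the two have nearly equal power when the SD without diabetes is small, and neither reaches 50% in any case.

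A reader might also infer that the 1-week result rests on HbA1c alone. It does not, since fasting glucose is in the same model and remains a usable 1-week outcome. The 12-week HbA1c analysis is untouched.

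Finally, home monitoring uses each participant's usual device, so the readings are not standardised. That is a reason for a careful summary rule or a stated reason for omission. It does not justify silence.

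**Conclusion.** The point holds as a gap between protocol and SAP and as a question of interpretation. Two parts need no numerical assumption: home glucose data are specified for both windows and have no analysis, and HbA1c enters a 1-week model that the protocol objective does not call for.

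The third part is conditional. If the protocol's no-effect hypothesis is right, the pooled estimate is 35-70% below the diabetic effect at a share of 65% down to 30%: 0.25-0.55 against 0.84, or 0.09-0.20 against about 0.3. The share is assumed. The 0.84 is an uncontrolled change in a small series and the 0.3 a difference of medians. The pooled estimate remains valid for the population that the protocol names. The plan should be amended, but the analysis as written is not invalid.

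**What to change.** In SAP 2.9:

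(a) Restrict HbA1c to Visits 3 and 9, with a note like those for NICOM and blood urea. Keep fasting glucose at both time points.

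(b) Add mean home glucose in T2D/PTDM participants as an outcome, comparing arms on the change from week -1 to the first week on study drug. State how unequal numbers of readings per day and per participant are averaged. Summarise the weeks on either side of the last dose (weeks 11-13) by the same rule. No objective concerns withdrawal, so that second summary should be descriptive.

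(c) Report model 1.1 fitted in T2D/PTDM participants, and in those without diabetes, beside the pooled estimate as part of the 2.9 result. The interaction test can stay in section 4.

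(d) Tabulate changes in glucose-lowering medication by arm, where recorded, beside the HbA1c result. The legible protocol tables do not show how dose changes are captured, so this should be confirmed first.

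The cost is SAP wording and modest analysis time; (a) to (c) need only measurements that the protocol already plans. The T2D/PTDM estimates will rest on fewer participants (about 7 to 16 per arm on the assumed shares), and home devices are not standardised. The change makes the glucose result easier to interpret but does not give it adequate power.

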## 4. Exploratory subgroup analyses

- 4.1. Compare diabetes vs non-diabetes status groups separately, and include test of interaction
  - a. Primary objectives
  - b. Secondary objectives
  - c. Exploratory objectives

## 5. Outcomes for pre-specified post-hoc analyses:

- 5.1. Urine adenosine will be normalized to urine creatinine
- 5.2. Relationship between proximal renal tubular natriuretic effects and markers of afferent arteriolar tone: proximal renal tubular natriuretic effects will be evaluated by lithium clearance FE(Li+); afferent arteriolar tone will be measured by urine adenosine normalized to urine creatinine.

# Statistical Analysis Plan (SAP)

- 0. Summary of baseline (Visit 3) demographic and clinical characteristics separated by dapagliflozin group and placebo group will be generated. Significance testing between-group will be performed. The following variables will be included:
  - Age, sex, weight, waist circumference, BMI, HbA1c, hemoglobin, fasting blood glucose
  - race (white/black/Hispanic/Asian/other)
  - SBP, DBP, MAP, HR
  - Mean eGFR calculated by CKD-EPI 2021 equation
  - UACR (median and IQR)
  - Concomitant medication use (ACEi, ARB, Diuretic, statin)

# 1. Analysis for the primary objective:

- 1.1. To assess dapagliflozin-related acute and chronic changes in the primary outcome of seated systolic blood pressure compared to placebo, linear mixed-effects models will be used. Two separate models will be fit. For acute change, the vector of outcomes will include the baseline and 1-week values (i.e. Visit 3 and Visit 4 values). For chronic changes, the vector of outcomes will include the baseline and 12-week values (i.e. Visit 3 and Visit 9 values). The covariates will include the visit and treatment-by-visit interaction; due to randomization, a covariate for the main effect of treatment will not be included. The treatment-by-time coefficient, its 95% confidence interval, and its p-value will be used to assess the effect of treatment.
- 1.2. We will repeat this analysis with:
  - a. Seated diastolic blood pressure as an outcome
  - b. Seated mean arterial pressure as an outcome

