
5. STUDY POPULATION

5.1 Inclusion Criteria

- 1. Male or females >18 years old \geq 6months after kidney transplantation;
- 2. In patients with T2D or PTDM, HbA1c <12.0%;
- 3. eGFR \geq 30 ml/min/1.73m² (as per the CKD-EPI equation⁷⁰);
- 4. BMI $\leq 45 \text{kg/m}^2$;
- 5. Blood pressure $\leq 160/90$ and $\geq 90/60$ at screening.

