5.3 Sample Size

The sample size is based on the primary endpoint of blood pressure. Currently, there is only one publication from our group with information available on the effect of SGLT2i on blood pressure reduction in KTR with diabetes. In this observational study of 10 KTR and simultaneous pancreas-kidney transplant recipients treated with canagliflozin, we reported a SBP decrease of $6.5 \pm 10 \text{ mmHg}^{63}$. Given the small sample size in our observational study, we believe the standard deviation would be smaller in a larger cohort. Blood pressure reduction with SGLT2 inhibition appear to be similar between patients with and without diabetes in non-transplant studies. We, therefore, estimated the sample size based on a SBP change of 6.5 mmHg with a standard deviation of 8 mmHg. Under the hypothesis that SGLT2i decreases SBP by $6.5 \pm 8 \text{ mmHg}$ compared to placebo with a two-sided alpha of 0.05 and 80% power, we calculate a sample size of n=48, with 24 randomized to dapagliflozin and 24 randomized to placebo. Assuming a 10% attrition rate, the final sample size required is 52 participants. This sample size is similar to those successfully used in previous studies⁷¹, and sufficient to measure secondary renal endpoints related to renal hemodynamic function⁷¹, natriuresis and arterial stiffness⁷²⁻⁷⁴. Based on previous studies, we anticipate an even sex distribution in each group.

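### SAP 1.1 leaves the pre-randomisation screening SBP out of the primary model; pre-specifying it as a covariate is a cheap efficiency gain, not the repair of an error

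*SAP*

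**What the plan says.** SAP 1.1 fits two linear mixed models to seated SBP, one for week 1 and one for week 12. On the second it says: "For chronic changes, the vector of outcomes will include the baseline and 12-week values (i.e. Visit 3 and Visit 9 values". SAP 1.2 repeats this for diastolic and mean arterial pressure. Two features matter here. First, "due to randomization, a covariate for the main effect of treatment will not be included", so the arms share one baseline mean and the model adjusts for Visit 3. Second, under the SAP's general model assumptions, "a participant-level random intercept will be included", which imposes equal correlation between all visits in the model.

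The SAP's baseline summary (item 0) also defines baseline as Visit 3. This agrees with Protocol 9.1.1, where baseline is Day 0.

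Protocol 5.1, item 5, makes eligibility depend on "Blood pressure $\leq 160/90$ and $\geq 90/60$ at screening". Protocol Table 2 marks vital signs at Visits 1, 3, 4, 6, 9 and 10, and randomisation at Visit 3. Every randomised participant should therefore have a Visit 1 SBP that treatment cannot have affected. The SAP's SBP model does not use it.

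**The concern.** One averaged seated reading is a noisy measure of a person's usual pressure. A second pre-randomisation reading normally carries further information about the week-12 value, and using it needs no new visit or patient.

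The trial is small, so precision has value. Protocol 5.3 plans for "a SBP change of 6.5 mmHg with a standard deviation of 8 mmHg", although the only transplant data it cites showed a larger spread (SD 10 in section 5.3; 10.8 in section 2.5 and Table 1). If the true SD of change is nearer 10.8, power on the primary endpoint is well below target and modest gains count for more. What is at stake is the width of the primary confidence interval, not its validity.

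**Working it through.** **Inputs from the documents (Protocol 5.3).** Effect 6.5 mmHg, SD of change 8 mmHg, "with a two-sided alpha of 0.05 and 80% power", "with 24 randomized to dapagliflozin and 24 randomized to placebo".

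**Plan's own figure.** SE of a difference in mean change = 8 × √(2/24) = 2.31 mmHg. Power = Φ(6.5/2.31 − 1.96) = 80.4%, so 24 per arm reproduces (a t-based calculation gives 78.7%). On attrition the plan says: "Assuming a 10% attrition rate, the final sample size required is 52 participants". 48/0.9 = 53.3, slightly more than 52; this does not affect the present point.

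**Assumed.** The correlations between visits: r39 (Visits 3 and 9), r13 and r19 (Visit 1 with each). The documents give none. Equal SD at each visit is also assumed.

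**Step 1: the SAP model as written.** With the SD of change fixed at 8, SE = 2.31 × √((1 + r39)/2).

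**Step 2: add Visit 1 as a covariate.** Let r13 = r19 = r1. Residual variance is multiplied by 1 − r1²(1 − r39)/[(1 − r1²)(1 + r39)]. If r1 = r39 = r this reduces to (1 + 2r)/(1 + r)². For r = 0.7: 2.4/2.89 = 0.830, so SE = 2.13 × √0.830 = 1.94.

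| r39 | SE (power), Visit 3 only | SE (power), plus equally correlated Visit 1 | SE cut, equal | SE cut, 0.8 × r39 | SE cut, 0.6 × r39 |
|---|---|---|---|---|---|
| 0.5 | 2.00 (90.1%) | 1.89 (93.2%) | 5.7% | 3.2% | 1.7% |
| 0.6 | 2.07 (88.2%) | 1.91 (92.4%) | 7.3% | 3.8% | 1.9% |
| 0.7 | 2.13 (86.3%) | 1.94 (91.8%) | 8.9% | 4.1% | 1.9% |
| 0.8 | 2.19 (84.3%) | 1.96 (91.2%) | 10.4% | 3.9% | 1.7% |

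Power here uses the normal approximation. An ANCOVA simulation (6,000 runs, 24 per arm), which counts the lost degree of freedom, gave 83.6% to 89.8% at r = 0.7 throughout, and 86.3% to 87.9% at r39 = 0.6, r1 = 0.48.

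**Step 3: a poor screening value.** At r39 = 0.7, r13 = 0.5, r19 = 0.4 the SE goes from 2.13 to 2.12. Simulated power was 84.7% without Visit 1 and 84.0% with it, so nothing is gained and little is lost.

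**Step 4: Visit 1 as an extra outcome row instead.** Under the random intercept, Visits 1 and 3 get the same weight b = ρ/(1 + ρ), with ρ approximated by the mean of the three correlations. The variance, in units of the visit variance, is 1 + 2b²(1 + r13) − 2b(r19 + r39), to be compared with 1 − r39² for Visit 3 only.

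- r39 = 0.76, r1 = 0.6: ρ = 0.653, b = 0.395, variance 0.425 against 0.422, or +0.6%. The covariate form gives −7.7%.
- r39 = 0.76, r1 = 0.5: ρ = 0.587, b = 0.370, variance 0.478 against 0.422, or +13% (SE +6%). The covariate form gives −4.5%.
- The Step 3 pattern: SE rises from 2.13 to 2.31 mmHg.

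**Step 5: larger SD of change.** With 10.8 and an assumed visit SD of 11.5–15, r39 = 1 − 10.8²/(2 × SD²) = 0.56–0.74. T-based power is 64–59% with Visit 3 only, and 70–68% with an equally correlated Visit 1.

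**The case against.** The strongest reply is that no error is shown. Baseline at Visit 3 is consistent across both documents, the estimator is valid, and the sample size does not depend on Visit 1. Adjusting for one protocol-defined baseline taken under controlled conditions is a reasonable choice. All of that stands.

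Nor is the screening reading shown to be comparable. Protocol 9.1.1 describes the three-reading seated method and lists Days 0, 7, 42, 84 and 91; screening is not among them. Protocol 9.3 puts the controlled diet before weeks 0, 1 and 12 only, and Table 2 marks those visits, not screening, as fasting clamp days. Eligibility also restricts the range of the screening value. These points lower the likely gain. They do not introduce bias, because the value precedes randomisation in both arms.

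A reader might infer that the trial sits at its power limit and is giving up free precision. The documents do not support that. The 80% in Protocol 5.3 rests on change scores, whereas the SAP model already adjusts for Visit 3 and, at the planned SD of 8, has about 84–90% power over the correlations tabulated. The gain is neither guaranteed nor entirely free. A reader might also suppose that an extra outcome row and a covariate are interchangeable; Step 4 shows that they are not under this SAP's covariance structure.

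**Conclusion.** The point holds as an efficiency improvement. SAP 1.1 leaves out a pre-randomisation SBP that every participant should have, and including it as a covariate would be unbiased. The reduction in SE lies between roughly 0 and 10%, depending on a correlation that the documents do not give. The upper end needs a screening reading as informative as Visit 3; the off-diet, possibly non-standardised screening visit makes the lower or middle part of the range at least as plausible. At the planned SD of 8, the power gain runs from about nil to 7 points. The primary analysis remains valid if nothing is changed.

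**What to change.** Before unblinding, add one sentence to SAP 1.1, carried over to 1.2 for diastolic and mean arterial pressure: the Visit 1 value of the same measure enters as a fixed covariate together with its interaction with visit, in both the week-1 and week-12 models. Keep the Visit 3-only model as a sensitivity analysis. Do not add Visit 1 as an outcome row under the random intercept.

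First confirm how the screening pressure was measured and that the recorded value is available for all randomised participants. The cost is one or two degrees of freedom and one sentence. Timing matters, because a covariate added after results are known would look selective.
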